10.2.4 Shipping Procedures

Peripheral blood specimens in SST Red Top and Streck tubes are to be shipped at ambient temperature day of collection Monday through Thursday via overnight courier.

The green top heparin tubes must be shipped the same day they are drawn because they must be processed the day after collection.

The laboratory is open Monday through Friday to receive specimens. Do not ship on Fridays or Saturdays, or the day before legal holidays. **Friday shipments are ill advised, similarly shipping before holidays is often problematic. The laboratory is closed Saturday, Sunday, and holidays.**

Ship using the CBPF's FedEx account using the FedEx on-line ship manager.

MD Anderson Cancer Center CBPF
[name]

[name]
[name]
[name]

Access to the FedEx shipping account for shipments to the ECOG-ACRIN CBPF at MD Anderson Cancer Center can only be obtained by logging onto fedex.com with an account issued by the ECOG-ACRIN CBPF. For security reasons, the account number will no longer be given out in protocols, over the phone, or via email. If your site needs to have an account created, please contact the ECOG-ACRIN CBPF by email at [contact]

An STS Shipping Manifest Form must be generated and shipped with all specimen submissions.

10.3 Central Laboratory: Processing and Routing

Pathology materials will be distributed to investigators for central pathology review and defined laboratory research studies described in Section [11](#).

Specimens submitted will be processed to maximize their utility for current and future research projects and may include, but not limited to, extraction of plasma, serum, DNA and RNA.

Specimens from patients who consented to allow their specimens to be used for future approved research studies, including residuals from the currently defined research studies, will be retained in an ECOG-ACRIN designated central repository. For this trial, specimens will be retained at the ECOG-ACRIN Central Biorepository and Pathology Facility. Specimens will be de-identified prior to distribution for any approved research projects.

If future use is denied or withdrawn by the patient, the specimens will be removed from consideration for use in any future study. Pathology materials may be retained for documentation purposes or returned to the site. All other specimens will be destroyed per guidelines of the respective repository.

10.4 ECOG-ACRIN Sample Tracking System

It is **required** (barring special circumstances) that all specimens submitted on this trial be entered and tracked using the ECOG-ACRIN Sample Tracking System (STS). As of June 2007, the software will allow the use of either 1) an ECOG-ACRIN username and password previously assigned (for those already using STS), or 2) a CTSU username and password.

When you are ready to log the collection and/or shipment of the specimens required for this study, please access the Sample Tracking System software by clicking <https://webapps.ecog.org/Tst>.

Important: Please note that the STS software creates pop-up windows, so you will need to enable pop-ups within your web browser while using the software. A user manual and interactive demo are available by clicking this link: <http://www.ecog.org/general/stsinfo.html>. Please take a moment to familiarize yourself with the software prior to using the system.

An STS generated Shipping Manifest must be generated and shipped with all specimen submissions.

Please direct your questions or comments pertaining to the STS to
[contact].

Study Specific Notes

Generic Specimen Submission Form (#2981v3) will be required only if STS is unavailable at time of specimen submission. Notify the laboratory of the shipment by faxing a copy of the completed form to the laboratory.

Retroactively enter all specimen collection and shipping information when STS is available.

10.5 **Sample Inventory Submission Guidelines**

Inventories of all specimens submitted will be tracked via the ECOG-ACRIN STS and receipt and usability verified by the receiving laboratory. Inventories of specimens forwarded and utilized will be submitted by the investigating laboratories to the ECOG-ACRIN Operations Office - Boston on a monthly basis in an electronic format defined by the ECOG-ACRIN Operations Office - Boston.

11. Specimen Analyses: Diagnostic Review and Research Studies

11.1 Central Diagnostic Review

The baseline diagnostic and surgical resection tumor tissue is required for central diagnostic review to determine patient evaluable for the trial and for central pathologic response assessments.

11.2 Ki67 and CD8+ infiltration

CD8 and Ki67 assays including staining, digital imaging and image analysis will be performed at MD Anderson Cancer Center and final result analysis will be performed under the direction of [name].

CD8 will be quantified as an H score as proposed and will include cytoplasmic and membranous staining. Focus will be placed on the tumor and peritumoral areas if needed and these areas of interest will be designated by the pathologist.

Ki67 nuclear staining is considered positive and not graded by staining intensity. The positively stained cells will be enumerated and the score will be generated by assessing both the total number and density of positive cells per square millimeter within the tumor/tumor bed area.

Ki-67 IHC in tumor cells will be graded as a percentage of total number of tumor cells with nuclear staining (to the nearest 10%) over 10 high powered fields (at 20X magnification).

Ki-67 alone can highlight any proliferating cell so this may overestimate the percent of proliferating cells. Focus will be placed on the on tumor cell rich areas as designated by pathologist.

Ki-67 IHC

Immunohistochemical studies will be performed on a Leica Bond autostainer, using the following antibodies: 3,3'-diaminobenzidine chromogen anti-Ki-67 (clone MIB-1; Dako, Carpinteria, CA; dilution 1:100).

CD8 IHC

Immunohistochemical studies will be performed on a Leica Bond autostainer, using the following antibodies 3,3'-diaminobenzidine chromogen anti-CD8 (Life Sciences Technologies MS457s; 1:25).

Image Analysis

Slides will be scanned at 20x magnification (Aperio Scanscope AT Turbo; Leica Biosystems). Image analysis software (Aperio ImageScope) measures the number of positive cells within designated areas. A Nuclear v9 algorithm is applied to determine Ki67 positivity. Also, given the relatively small size of immune cells, a modified version of the Nuclear v9 algorithm will be applied as a basis for CD8 immune marker positivity, with the intensity thresholds adjusted manually to remove background artifacts and to account for variable differences in cell size.

For each region of interest designated, the numbers of positive cells will be tabulated, and the total number of positive cells will be divided by the total area (mm^2) in which cells will be counted. The result will be reported as number of IHC+ cells/ mm^2 .

Specimens will be examined with a minimum of 4 quadrant sections of viable tumor to be submitted for pathological examination. The whole specimen will be evaluated and each slide divided into 4 quadrants. At 20x, intratumoral, peritumoral and perivascular mononuclear cell infiltrates will be enumerated, per published protocols [Tanhini, et al, PLOS One 9(2):1-8].

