6.1.5 Response Criteria

6.1.5.1 Pathologic Response Rate (pCR)

Pathologic complete response (pCR) is defined as the absence of residual melanoma in resected tissue as assessed on local pathology review. These will have central review retrospectively.

- **Pathologic complete response (pCR)**
 - Complete absence of viable tumor in the treated tumor bed
- **Major PR**
 - $\leq 10\%$ of viable tumor in the treated tumor bed
- **Partial pathologic response (pPR)**
 - Less than or equal to 50% of the treated tumor bed is occupied by viable tumor cells
- **Pathologic non-response (pNR)**
 - Greater than 50% of the treated tumor bed is occupied by viable tumor cells

Pathologic Response	Remarks
pCR	Complete absence of viable tumor in the treated tumor bed
Major PR	$\leq 10\%$ of viable tumor in the treated tumor bed
pPR	Less than or equal to 50% of the treated tumor bed is occupied by viable tumor cells
pNR	Great than 50% of the treated tumor bed is occupied by viable tumor cells
	Patients that demonstrate objective RECIST progression, they will be classified at pathologic NR

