9.4 Secondary Lab Endpoints

CD8+ T cell infiltration:

Given the expected 57% pCR rates, there will be at least 13 responders and 10 non - responders among cases with samples. If the standardized change ((mean value for post-treatment samples – mean value for pre-treatment samples)/sd) is at least 1.1 for responders vs. non-responders, there will be at least 81% power for this comparison. If the post-treatment samples are not available, during-treatment samples will be used. This is based on the two-sample t-test using two-sided type I error rate of 0.1. If normality assumption is not appropriate, Wilcoxon rank sum test will be used during the analysis. Using the median change value, cases will be divided to high and low change groups.

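### Section 11.2 asks for viable tumour that a pCR resection lacks, and no section fixes one scoring region, so region or time point can differ by group in the late CD8-change comparison

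*Combined protocol and SAP*

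**What the plan says.** **Specimen rule.** Section 11.2 says "Specimens will be examined with a minimum of 4 quadrant sections of viable tumor to be submitted for pathological examination". The next sentence says "The whole specimen will be evaluated and each slide divided into 4 quadrants", and intratumoral, peritumoral and perivascular infiltrates are then to be counted.

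**Response definition.** Section 6.1.5.1 (and 6.1.1) defines pCR as "Complete absence of viable tumor in the treated tumor bed".

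**Region for CD8.** The rationale (1.6), hypothesis 1.8.2.4, objective 2.3.1, the endpoint list in 9.1 and the analysis plan in 9.5 all refer to tumour or tumour bed. The CD8 paragraph of 11.2 is narrower: "Focus will be placed on the tumor and peritumoral areas if needed and these areas of interest will be designated by the pathologist". The Ki-67 paragraph of 11.2 names the tumour bed; the CD8 paragraph does not.

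**Scale.** Section 11.2 says "CD8 will be quantified as an H score as proposed and will include cytoplasmic and membranous staining". Under image analysis it says "The result will be reported as number of IHC+ cells" per square millimetre.

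**Comparison.** Section 9.4 expects that "there will be at least 13 responders and 10" non-responders will have samples. It claims at least 81% power for a 1.1 SD difference in change, with a two-sample t-test at two-sided 0.1. Section 9.5 compares pre- to post-treatment change by pCR status with the Wilcoxon rank sum test.

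**Substitution.** Section 9.4 uses during-treatment samples when post-treatment samples are not available. Under secondary imaging aim #3, section 9.7.3.2 notes that the week-2 biopsy is not mandatory and that few are expected.

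**The concern.** The grouping variable in this comparison is pCR, and pCR is defined by the absence of the tissue that one sentence of 11.2 asks for. One whole comparison group therefore fails that sentence by definition. The wording that permits tumour bed shows that such resections can be scored, but not where, or that non-pCR resections and baseline samples are scored in the same place. The choice is left to the pathologist, slide by slide.

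Two things could follow. If pCR resections are scored in the regressed bed and non-pCR resections in tumour, the region is tied to the outcome group. If pCR resections are treated as unscorable, they may count as not available under 9.4. Responders would then contribute week-2 change while non-responders contribute change at resection, so the time point is tied to the outcome group. In either case a difference in late CD8 change, or its absence, could not be attributed to CD8 biology alone. At stake is the late-change part of hypothesis 1.8.2.4. The primary pCR endpoint is not affected.

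The two scales are a separate matter. An H score and a cell density are not interchangeable, and the analysed variable is left open.

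**Working it through.** **1. The sections side by side.**

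| Question | What the documents give |
|---|---|
| Tissue asked for (11.2) | At least four quadrant sections of viable tumour |
| Tissue in a pCR resection (6.1.5.1) | No viable tumour |
| Region allowed (1.6, 1.8.2.4, 2.3.1, 9.1, 9.5) | Tumour or tumour bed |
| Region named for CD8 in the assay text (11.2) | Tumour, and peritumoral areas if needed, as the pathologist designates |
| Same region in pCR and non-pCR resections | Not stated |
| Whether a pCR resection counts as not available (9.4) | Not stated |
| Analysed CD8 scale (11.2) | Two named, none chosen |

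**2. The plan's own power figure.** Inputs from 9.4: n₁ = 13, n₂ = 10, d = 1.1 SD, two-sided α = 0.10, t-test. The split matches 57% of 23 cases: 0.57 × 23 = 13.1.

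- Noncentrality = d / √(1/n₁ + 1/n₂) = 1.1 / √(1/13 + 1/10) = 1.1 / 0.4206 = 2.615
- df = 13 + 10 − 2 = 21; critical t = 1.721
- Power = P(|T| > 1.721), with T noncentral t on 21 df = 81.2%

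The stated figure of at least 81% reproduces. On the same inputs with normal data, the Wilcoxon test planned in 9.5 has about 77.5% power (8,000 simulated samples).

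**3. Sensitivity A: only some pCR cases scorable.** The formula is the same, with n₂ = 10 and d = 1.1. The numbers scorable are assumptions; the documents give none.

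| Scorable pCR cases | Noncentrality | Power |
|---|---|---|
| 13 | 2.615 | 81% |
| 10 | 2.460 | 76% |
| 6 | 2.130 | 65% |
| 4 | 1.859 | 54% |

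With no scorable pCR resection and no week-2 substitute, there is no comparison.

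**4. Sensitivity B: all 13 and 10 scored, but in different regions.** Suppose region alone shifts the measured change by δ SD between the groups. The shift sizes are assumptions; the documents give no size for a region effect.

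| δ | Rejection rate with no true effect (nominal 10%) |
|---|---|
| 0.3 | 18% (noncentrality 0.713) |
| 0.5 | 31% (noncentrality 1.189) |

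The shift can also work the other way. If δ = 0.5 opposes a true 1.1 SD effect, the net difference is 1.1 − 0.5 = 0.6 SD and power falls to 40%.

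The calculations in steps 3 and 4 use the t-test, to match 9.4.

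**The case against.** The strongest reply is that the viable-tumour sentence concerns specimen sampling and should not be read as the whole scoring rule. Five other places in the protocol allow the tumour bed, and the very next sentence of 11.2 has the whole specimen evaluated. That stands. A reader might infer that CD8 scoring requires viable tumour and so no pCR patient can be scored; the documents do not support this.

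A reader might also infer that the comparison certainly contrasts compartments instead of treatment effects. That goes too far. A compartment contrast arises only if the bed is scored in pCR cases and tumour in the others. A strict viable-tumour rule would instead produce missing values or week-2 substitutes. The documents leave both routes open and settle neither.

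Other parts of the reply also hold:

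- The two scales apply to both groups alike, so they cannot create a group difference. The reporting sentence also leans towards cells/mm². What remains is an unnamed analysis variable.
- Hypothesis 1.8.2.4 also covers baseline CD8 and early on-treatment change, and links to DFS and OS. Baseline and early change do not depend on pCR resections, so it would be wrong to conclude that the whole hypothesis is unanswerable.
- No planned figure is wrong; the losses in steps 3 and 4 are illustrations.
- Section 11.2 points to published protocols, which may define regions. They are not reproduced in the document.

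What the reply does not supply is a sentence making the scored region the same in both groups, or one saying how 9.4's substitution treats a pCR resection.

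**Conclusion.** The point holds in limited form. One sentence of 11.2 cannot be met by any pCR resection, the wider wording permits the tumour bed without requiring a common region, and 9.4's substitution rule does not say whether a pCR resection is an available sample. For late CD8 change by pCR status, region or time point can therefore be confounded with group, and the plan as written cannot separate either from a true CD8 difference. Separately, the analysed CD8 scale is not named.

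This conclusion rests on the text alone. Its numerical size is not known from the documents: 65% power assumes 6 scorable responders, and 18% to 31% false positives assume a pure region shift of 0.3 to 0.5 SD. The 81% in 9.4 is correct for its inputs. This is a secondary correlative comparison, so the wording should be changed, but the main result of the trial does not depend on it.

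**What to change.** In 11.2:

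1. Limit the viable-tumour requirement to the baseline and week-2 biopsies.
2. Score the whole treated tumour bed (viable tumour plus regression area) in every resection, whatever the response.
3. Name CD8+ cells/mm² as the analysed scale and delete the H score.

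In 9.4:

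4. State that a pCR resection counts as an available post-treatment sample, so a week-2 sample does not replace it.
5. Report week-2 change descriptively only, because few optional biopsies are expected.

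The cost is a wording change in two sections and in the laboratory's scoring instructions. Slide scanning and digital counting are already planned in 11.2.

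The change reduces the problem but does not remove it. Tumour-bed density is not purely intratumoral. A pCR bed is all regression area, while a non-pCR bed still holds viable tumour, and baseline tissue is tumour in both groups. The late-change result should carry that caveat when it is interpreted.

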Appendix I

Pathology Submission Guidelines

The following items are included in Appendix I:

1. Guidelines for Submission of Pathology Materials
(instructional sheet for Clinical Research Associates [CRAs])
2. List of Required Materials for EA6183
3. ECOG-ACRIN Generic Specimen Submission Form (#2981v3)

Guidelines for Submission of Pathology Materials

The following pathology materials are to be submitted within one (1) month of registration or collection. If these criteria cannot be met, please contact the ECOG-ACRIN CBPF ([contact]) to obtain alternative submission requirements.

Adequate patient identifying information must be included with every submission to retain chain of custody. It is strongly recommended that full patient names be provided. The information will be used only to identify patient materials, and will expedite any required communications with the institution (including site pathologists).

Pathology Submissions:

Mandatory:

- Representative formalin-fixed paraffin-embedded (FFPE) tumor tissue blocks from the baseline diagnostic biopsy

Submit the following:

- all available tumor tissue blocks, OR
- two (2) representative unstained FFPE slides per block, OR
- one (1) representative H&E slide and one (1) representative unstained slide per block.

NOTE: If the patient has consented to undergo a research biopsy to obtain tumor tissue for laboratory research studies, material captured prior to start of treatment may be submitted as outlined below in lieu of archived FFPE. If a research biopsy from consenting patients is submitted for the mandatory baseline diagnostic submission, an FFPE block must be submitted.

- Representative formalin-fixed paraffin-embedded (FFPE) tumor tissue blocks from the surgical resection biopsy

Submit the following:

- all available tumor tissue blocks, OR
- two (2) representative unstained FFPE slides per block, OR
- one (1) representative H&E slide and one (1) representative unstained slide per block.

NOTE: A three-dimensional macroscopic measurement of the largest grossly positive identified lymph node should be provided in the gross description accompanying the specimen. If the largest grossly positive lymph node measures < 5 cm in greatest dimension, then each grossly positive lymph node should be submitted entirely at 2 mm serially sectioned intervals. For any grossly positive lymph node measuring > 5 cm in greatest dimension, representative sections of the largest lymph nodes may be utilized to avoid oversampling. Following serial sectioning of each lymph node, for those nodes > 5 cm, sections representing a complete cross section of the entire surface area should be submitted per 1 cm of each grossly positive lymph node. Sections submitted should include grossly obvious tumor. All grossly positive lymph nodes < 5 cm in specimens (where the largest node(s) exceeds 5 cm) should be submitted entirely.

From Consenting Patients:

Research Biopsies

- Representative formalin-fixed paraffin-embedded (FFPE) tumor tissue blocks from baseline following step 1 registration (prior to treatment) and two weeks post treatment biopsy.

NOTE: This baseline research biopsy is requested only if there is no material available from a prior procedure performed within two (2) months of imaging.

Biopsies to obtain specimens for research must be determined to be minimal risk prior to performance. Tumor tissue specimens are to be obtained from the target lymph node metastases, with or without image guidance. Types of biopsies are to include: 3-4 (1-2 cm in length), 14-16 or 18-gauge core biopsies, or small incisional biopsies (tumor biopsy at least 4-5 mm in diameter) such that the smallest dimension of the residual tumor after initial biopsy would be at least 1 cm [minimal size of single tumor is at least 2 cm in smallest dimension]. It is suggested that core biopsies be submitted separately into individual tissue blocks.

NOTE: Reimbursement guidelines for research biopsies are outlined in [Appendix XI](#).

Forms and Reports:

The following items are to be included with the pathology materials:

- Institutional Diagnostic and Surgical Pathology Report
- ECOG-ACRIN Generic Specimen Submission Form (#2981v3) [if STS is unavailable]
- Sample Tracking System (STS) Shipping Manifest Form
- Immunological study reports, if available

Mail pathology materials to:

ECOG-ACRIN Central Biorepository and Pathology Facility
MD Anderson Cancer Center

Institution Instructions: This form is to be completed and submitted with **all specimens** ONLY if the Sample Tracking System (STS) is not available. **Use one form per patient, per time- point.** All specimens shipped to the laboratory must be listed on this form. Enter all dates as MM/DD/YY. Keep a copy for your files. Retroactively log all specimens into STS once the system is available. **Contact the receiving lab to inform them of shipments that will be sent with this form.**

Protocol Number _____ Patient ID _____ Patient Initials Last _____ First _____

Date Shipped _____ Courier _____ Courier Tracking Number _____

Shipped To (Laboratory Name) _____ Date CRA will log into STS _____

FORMS AND REPORTS: Include all forms and reports as directed per protocol, e.g., pathology, cytogenetics, flow cytometry, patient consult, etc.

Required fields for all samples			Additional fields for tissue submissions				Completed by Receiving Lab
Protocol Specified Timepoint:							
Sample Type (fluid or fresh tissue, include collection tube type)	Quantity	Collection Date and Time 24 HR	Surgical or Sample ID	Anatomic Site	Disease Status (e.g., primary, mets, normal)	Stain or Fixative	Lab ID

Fields to be completed if requested per protocol. Refer to the protocol-specific sample submissions for additional fields that may be required.

Leukemia/Myeloma Studies:	Diagnosis	Intended Treatment Trial	Peripheral WBC Count (x1000)	Peripheral Blasts %	Lymphocytes %
Study Drug Information:	Therapy Drug Name	Date Drug Administered	Start Time 24 HR	Stop Time 24HR	
Caloric Intake:	Date of Last Caloric Intake		Time of Last Caloric Intake 24HR		

CRA Name _____

CRA Phone _____

CRA Email _____

Comments

9/12/14

A Phase II Neoadjuvant Study of Encorafenib With Binimetinib in Patients With Resectable Locoregional Metastases From Cutaneous or Unknown Primary Melanoma (Stages III N1B/C/D)

